6.2.1.4 Concomitant therapies

Relevant concomitant diagnoses and/or therapies present at trial entry and/or during screening and relevant to the patient's safety during the trial as judged by the Investigator will be recorded in the eCRF (see Section 4.2.2 for details on concomitant medications). Post-trial therapy for advanced or metastatic disease will also be documented.

6.2.2 Treatment period

Please refer to [Flow Chart 1](#) (dose escalation) and [Flow Chart 2](#) (dose expansion) for a detailed presentation of each visit during the treatment period.

6.2.3 Follow-up period and trial completion

6.2.3.1 End-of-treatment visit

The EOT visit will be performed after permanent discontinuation of trial medication for any reason, as soon as possible, but no later than 7 days after permanent discontinuation of the trial medication or when the Investigator decided with the patient to permanently discontinue the trial medication or became aware that the trial medication had been terminated.

The assessments of the EOT visit will then be performed instead of at the next planned visit. If the patient finishes active treatment without having PD, tumour assessment/imaging must be performed at the time of treatment discontinuation, unless it has been done within the past 4 weeks.

For patients still on treatment with ezabenlimab at the time point of this protocol amendment, the investigators are asked to prepare for discontinuation of patients from the current investigational treatment with ezabenlimab and to switch them to alternative available treatment options outside of the current protocol no later than by the final availability of ezabenlimab in August 2023 the latest. After this date treatment with the ezabenlimab will no longer be available.

For these patients only EOT visit will be performed. 30-day post-treatment safety visit as well as Progression-free survival visits are not applicable.

6.2.3.2 30-day post-treatment safety visit

The safety follow-up visit is performed 30 (+2) days after permanent discontinuation of the trial medication. The information collected at this visit must include all new AEs that occurred after the EOT visit, and a follow-up of AEs ongoing at EOT.

A patient will be considered as having completed the trial if he/she discontinues because of PD and has performed the safety follow-up visit 30 days after EOT, or was lost to follow up, or withdrew consent for further evaluation at the EOT visit. If the patient discontinues for any other reason, he/she will be considered as withdrawn.

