Main criteria for inclusion:	
Phase Ia Dose Escalation – adult patients with a confirmed diagnosis of advanced, unresectable, and/or metastatic solid tumours (any type) who have received all therapy known to confer clinical benefit (including anti-PD-1 therapies, if relevant and if the last dose of the prior anti-PD-1 was received more than 60 days prior to starting study drug), or for whom no therapy of proven efficacy exists, or who are not amenable to standard therapies
 
Phase Ib Dose Expansion – adult patients with a confirmed diagnosis of select advanced, unresectable, and/or metastatic solid tumours who are anti-PD-1/PD-L1 naïve but have failed conventional treatment (excluding anti-PD-1/PD-L1 treatment), or for whom no therapy of proven efficacy exists, or who are not amenable to standard therapies.
 
All patients must have measurable lesions according to Response Evaluation Criteria in Solid Tumours (RECIST) v1.1 and/or Immune-Related Response Evaluation Criteria in Solid Tumours (iRECIST).
 
Additional specific criteria for the individual expansion cohorts include:
 
- Cohort 4: Advanced and/or metastatic solid tumours including NSCLC, bladder cancer, melanoma, gastric cancer, ovarian cancer, TNBC, and RCC- Cohort 5: Patients with tumours that are TMB-high: any tumour with TMB-high status (>10 mutations/Mb), excluding those that are MSI-high (TMB and MSI status based on any validated test)- Cohort 6: Patients with squamous cell cervical, anal, and skin tumours that are refractory to standard therapies.- Cohort 7: Patients with recurrent HPV-positive, or HPV-negative, vaginal or VSCC	

Name of company:	Boehringer Ingelheim	
Name of finished product:	N.A.	
Name of active ingredient:	BI 754091	
Protocol date: 22 Sep 2016	Trial number: 1381.1	Revision date: 07 March 2023
Test product:	BI 754091	
Dose:	Phase Ia Dose Escalation : starting dose is 80 mg (1 mg/kg for a 80-kg person) once every 3 weeks (q3w) Phase Ib Dose Expansion : the RP2D established in Phase Ia	
Mode of administration:	Intravenous infusion	
Duration of treatment:	BI 754091 will be given on Day 1 of 21-day cycles for up to 1 year, or until progressive disease (PD) or unacceptable toxicity in the absence of other withdrawal criteria. If the patient is benefiting clinically at 1 year, he/she may continue after a case by case review with the sponsor, but no longer than 31 August 2023.	

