 - Another biopsy (optional) should be taken upon PD (according to RECIST v1.1 and iRECIST), if possible. An optional biopsy should also be taken if a patient has stable disease over 3 subsequent disease assessment periods.
- m Tumour assessments should be done according to RECIST v1.1 and iRECIST and should include CT/PET scans of the chest and abdomen and, if clinically indicated, imaging of any other known or suspected sites of disease (e.g., pelvis, brain) using an appropriate method (CT/PET scan or MRI). The same radiographic procedure must be used throughout the trial. In case of suspected (but not confirmed) bone metastasis at screening, tumour assessment at screening should include a bone scan. If bone lesions are already known or confirmed at screening, correlative imaging (X-ray or CT scan) should be performed. Correlative imaging should then be repeated at each tumour assessment (see Section 5.2.1 for more detail). Assessments will be performed by the Investigator at screening and every 2 cycles (6 weeks) for the first 6 months of treatment and once every 3 cycles (9 weeks) thereafter until PD or start of further treatment for disease, and at the discretion of the Investigator.
- n If the decision is made to permanently discontinue BI 754091 during a scheduled visit, the EOT visit assessments should be performed instead of the scheduled visit.
- o **Patients enrolled in Protocol Version 4.0 (expansion Cohort 4 and higher):** Additional overall survival (OS) and progression-free survival (PFS) follow-up visits after the 30-day safety follow-up visit will be performed once every 12 weeks at least (by telephone) until death, loss to follow-up, withdrawal of consent, or end of the whole trial. **Patients enrolled in Protocol Version 3.0 and earlier (expansion Cohort 1,2,3):** Additional PFS follow-up visits after the 30-day safety follow-up visit will only be performed for patients who did not progress on treatment. These will be performed once every 12 weeks at least (by telephone) until PD, introduction of a new anti-cancer treatment, death, loss to follow-up, withdrawal of consent, or end of the whole trial.
- p The patients will not be required to go to the clinic on Cycle 4 Days 2 and 15 and Cycle 8 Days 2 and 15.
- q Only patients completed the activity up to until the cut off date for the primary report. All remaining patients will undergo EOT and 30 days visits safety procedures only.

TABLE OF CONTENTS

TITLE PAGE	1

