3.3.4.2 Discontinuation of the trial by the sponsor

Boehringer Ingelheim reserves the right to discontinue the trial overall or at a particular trial site at any time for the following reasons:

1. Failure to meet expected enrolment goals overall or at a particular trial site

Proprietary confidential information © 2023 Boehringer Ingelheim International GmbH or one or more of its affiliated companies

2. Emergence of any efficacy/safety information invalidating the earlier positive benefit-risk-assessment that could significantly affect the continuation of the trial
3. Violation of Good Clinical Practice (GCP), the clinical trial protocol (CTP), or the contract disturbing the appropriate conduct of the trial.
4. Completion of treatment by all patients and the sponsor determines that sufficient survival data has been collected.
5. Termination of the development program by the sponsor .

In case the trial is ended by the sponsor, the available clinical trial data will be analyzed and reported approximately one year after the last patient has been enrolled. Patients who are still being treated with BI 754091 when the primary report of the trial is being prepared, will be kept on treatment in this trial and finalize the clinical observation period by 31 August 2023 at the latest. Data of those patients will then be reported in a revised report and it will be noted in the primary report that such a revised report will be written.

The Investigator / the trial site will be reimbursed for reasonable expenses incurred in case of trial termination (except in case of the third reason).

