5.3.6.8 Adverse event collection and reporting

5.3.6.8.1 Adverse event collection

The Investigator shall maintain and keep detailed records of all AEs in their patient files.

A schema of the safety follow-up period is presented in [Figure 5.3.6.8.1: 1](#). The following must be collected and documented on the appropriate eCRF by the Investigator:

- From signing the ICF onwards until the end of treatment (including the Residual Effect Period [REP]; a period of 30 days after the last dose of trial medication):
-all AEs (non-serious and serious) and all AESIs.
- After the EOT (including the REP) until the individual patient's end of trial:
-all related SAEs and all related AESIs.
- After the individual patient's end of the trial, the Investigator does not need to actively monitor the patient for AEs, but should only report relevant SAEs and relevant AESIs of which the Investigator may become aware of.

The rules for Adverse Event Reporting exemptions still apply.

[figure not shown]

Figure 5.3.6.8.1: 1 Safety follow-up schema

All AEs which occurred through the treatment phase and throughout the REP will be considered as on treatment; please see [Section 7.3.4](#). Events which occurred after the REP will be considered as post-treatment events.

Adverse event reporting to the sponsor and timelines

The Investigator must report SAEs, AESIs, and non-serious AEs that are relevant for the reported SAE or AESI, on the BI SAE form via secure e-mail connection or via fax immediately (within 24 hours) to the [REDACTED]

- Secure email [REDACTED] SAE mailbox: [REDACTED] or
- Fax [REDACTED] safety fax number: [REDACTED]

For sites outside of the US, country-specific fax numbers will be provided in the ISF/Study reference manual.

The same timeline applies if follow-up information becomes available. On specific occasions, the Investigator could inform the [REDACTED] upfront via telephone by calling the [REDACTED] SAE reporting phone number ([REDACTED]). This does not replace the requirement to complete and fax the BI SAE form.

With receipt of any further information to these events, a follow-up SAE form has to be provided. For follow-up information the same rules and timeline apply as for initial information.

Information required

For each AE, the Investigator should provide the information requested on the appropriate eCRF pages and on the BI SAE Report form. The Investigator should determine the causal relationship to the trial medication.

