6. INVESTIGATIONAL PLAN

6.1 VISIT SCHEDULE

The trial consists of 2 parts. The first part is a dose-escalation phase (Phase Ia) to determine the MTD and the recommended dose for the Phase Ib dose expansion. The schedule shown to have a more favourable safety, PK, and biomarker profile will be chosen to be further investigated in the expansion phase. The second part (Phase Ib) is an expansion phase to further evaluate safety, efficacy and PK profile of BI 754091, as well as biomarker values as a result of treatment.

Patients meeting the inclusion and exclusion criteria for the part they are participating in and who have given their written ICF, are eligible for participation in the trial. Patients will visit the clinical site at the time points specified in [Flow Chart 1](#) (dose escalation) and [Flow Chart 2](#) (dose expansion). If a patient misses a scheduled visit, and reports to the Investigator between the missed visit and the next scheduled visit, the assessments for the missed visit must be done with the actual date and the reason must be given for the delayed visit. For the biopsies and PK sampling procedures of Cycle 1, the patient must however still be under treatment and not in a treatment break period in order to perform the evaluations planned for the missed visit. The next visit must then take place at the scheduled time after the first administration of the trial drug in the respective treatment cycle.

Once the decision for any reason is made for a patient to stop the treatment with BI 754091, an EOT visit must occur as soon as possible (preferably within 7 days). After the EOT visit, the patient must undergo a follow-up evaluation 30 (+2) days after the last BI 754091 administration.

The trial will be conducted according to the principles of Good Clinical Practice (GCP).

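### Section 6.2.3.1 drops the 30-day safety visit for patients still on drug in March 2023, while other current text requires it and AE/DLT collection still runs to last dose + 30 days

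*Protocol*

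**What the plan says.** Section 6.2.3.1 of the current protocol (version 8.0, 07 March 2023) asks investigators to move patients still on ezabenlimab to other treatment by the end of August 2023. It then adds: "For these patients only EOT visit will be performed. 30-day post-treatment safety visit as well as Progression-free survival visits are not applicable".

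Other current text says something different:

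- Flow Chart 2, footnote q, on patients who continue beyond the primary-report cut-off: "All remaining patients will undergo EOT and 30 days visits safety procedures only".
- Section 6.1, without exception: after EOT, "the patient must undergo a follow-up evaluation 30 (+2) days after the last BI 754091 administration".
- Section 6.2.3.2, on the content of the 30-day visit: it "must include all new AEs that occurred after the EOT visit, and a follow-up of AEs ongoing at EOT".

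The collection and analysis period was not changed. Section 5.3.6.8.1 requires all AEs and AEs of special interest (AESIs) through the residual-effect period, defined as "a period of 30 days after the last dose of trial medication". Section 5.3.6.5.1 makes every DLT an AESI. Protocol 7.3.4, SAP 5.1 (the Phase Ib primary DLT endpoint) and SAP Table 6.1: 1 use the same end point of last dose + 30 days.

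On dates, the Synopsis lets patients continue beyond one year, "but no longer than 31 August 2023". Section 3.3.4.2 says those still treated when the primary report is prepared will "finalize the clinical observation period by 31 August 2023 at the latest", and "Data of those patients will then be reported in a revised report".

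**The concern.** Two things do not fit together. First, a site working from the flow chart or Section 6.1 would hold the 30-day visit, and a site working from Section 6.2.3.1 would not. Second, if 6.2.3.1 is followed, no contact is scheduled between EOT and day 30, yet that interval still counts as on-treatment for AEs and DLTs.

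The patients affected are stopping a checkpoint inhibitor and moving to other therapy. SAP 7.8.1 recognises that immune-mediated events can begin more than 30 days after treatment and plans extra tables for them. Without a scheduled contact, late AEs, AESIs and DLTs would be captured only if the patient or the new treating team brings them to the investigator's attention.

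**Working it through.** There is no planned figure to reproduce. The check is a comparison of the texts, followed by simple date arithmetic.

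**Step 1: what happens after EOT, by section**

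| Source | Instruction or window |
|---|---|
| 6.2.3.1 | EOT only; no 30-day visit, no PFS visits |
| Flow Chart 2, footnote q | EOT and 30-day safety procedures |
| 6.1 | 30 (+2)-day evaluation mandatory |
| 6.2.3.2 | That visit collects new AEs and follows ongoing ones |
| 4.2.2 | Concomitant therapy recorded up to the 30-day visit |
| 5.3.6.8.1, 7.3.4, SAP 5.1, SAP Table 6.1: 1 | Window runs to last dose + 30 days |

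The first row conflicts with the second and third. It also removes the collection point in the fourth and the stop point in the fifth, and leaves the window in the last row unchanged.

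Section 5.3.6.8.1 adds that active AE monitoring is not needed after a patient's individual end of trial. If EOT is the last visit, a site could take EOT as that end and stop monitoring inside the 30 days.

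**Step 2: days without a scheduled contact**

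Uncovered days = 30 − (days from last infusion to EOT). The protocol times EOT from discontinuation, or from the decision to discontinue, so the EOT days below are assumptions.

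- EOT on day 7: 30 − 7 = 23 days.
- EOT in place of the next three-weekly visit, day 21: 30 − 21 = 9 days.
- EOT seven days after a decision made on day 21, day 28: 30 − 28 = 2 days.
- EOT after day 30, for example after a dose delay (Section 4.1.4 allows up to 6 weeks): 0 days.

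**Step 3: calendar, with 31 August 2023 as both the last possible dosing date and the end of observation**

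- Latest infusion whose day 30 falls by 31 August: 31 August − 30 days = 1 August.
- With uninterrupted three-weekly dosing up to the limit, the last infusion falls between 11 and 31 August, because an infusion on 10 August would be followed by another on 31 August.
- Day 30 then falls between 11 August + 30 = 10 September and 31 August + 30 = 30 September, which is 10 to 30 days after the stated end of observation.
- Latest 30 (+2)-day contact: 31 August + 32 days = 2 October 2023.

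**The case against.** The strongest reply is that 6.2.3.1 is a deliberate exception for a named group during close-out of a terminated programme, so it overrides the general rule in 6.1 and agrees with the August cut-off in 3.3.4.2. Footnote q was added in Amendment 6 mainly to stop PK and biomarker sampling. The reporting duty does not depend on the visit: AEs and AESIs must still be documented to day 30, serious events and AESIs must be reported within 24 hours, and ongoing events must be followed to resolution or adequate characterisation. The 23-day gap is the upper end of an assumed range, and the term for the observation period in 3.3.4.2 is not defined. Only Cycle 1 DLTs drive escalation, and no hypothesis is tested.

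Much of this stands. The waiver does look intended. The available amendment log does not reach an entry for 6.2.3.1, so nothing is inferred about a missing rationale. The duty to report is intact, and so is follow-up of events ongoing at EOT. The main exposure is new events between EOT and day 30.

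What does not stand is the view that reading the specific rule over the general one settles the matter. Footnote q is itself a specific rule for remaining patients, and its current wording keeps the 30-day safety procedures. Even if 6.2.3.1 prevails, the protocol then requires complete AE collection over a period in which it schedules no contact. Agreement between 6.2.3.1 and 3.3.4.2 does not help, because neither agrees with the 30-day window.

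**Conclusion.** The concern holds. The current protocol gives conflicting instructions on the 30-day safety visit, and the version in 6.2.3.1 removes the scheduled means of collecting AEs over part of the period the analysis covers. The uncovered part ranges from 0 to 23 of the 30 days per patient, depending on the assumed EOT timing. The calendar overrun of 10 to 30 days assumes uninterrupted three-weekly dosing up to the limit and a literal reading of 3.3.4.2.

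The consequence is possible under-ascertainment of AEs, AESIs and DLTs. It affects only patients still on treatment in 2023, whose number is not stated, and only the revised report, where analyses are descriptive. Dose-escalation decisions are unaffected. The effect is probably small, but the point concerns safety follow-up and costs little to correct, so the change should be made.

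**What to change.** - In 6.2.3.1, keep a 30 (+2)-day safety visit or telephone contact for these patients, covering AEs, SAEs, AESIs including DLTs, and follow-up of AEs ongoing at EOT. Waive only the PFS visits. This brings the section into line with footnote q and 6.1.
- In 3.3.4.2, state that this contact may take place after 31 August 2023.
- Leave the SAP window at last dose + 30 days. Shortening it to match the waiver would make these patients' on-treatment period differ from everyone else's.

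The cost is one sentence in each of the two sections and one contact per remaining patient, at the latest on 2 October 2023. No further drug supply and no SAP change are needed.

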6.2.3.3 Progression-free survival visits

Additional follow-up visits after the 30-day safety follow-up visit will only be performed for patients who did not progress on treatment. These will be performed once every 12 weeks at least (by telephone) until PD, introduction of a new anti-cancer treatment, death, loss to follow-up, or end of the whole trial as specified in Section 3.3.4.2.

6.2.3.4 Overall survival visits

Additional follow-up visits after the 30-day safety follow-up visit will be performed for patients that enrolled in Protocol Version 4.0 and beyond. These will be performed once every 12 weeks at least (by telephone) on the same schedule as PFS survival visits until death, loss to follow-up, or end of the whole trial as specified in Section 3.3.4.2. If the sponsor determines that enough OS data has been collected from select cohorts, sites could be instructed to discontinue OS visits for those cohorts.

7. STATISTICAL METHODS AND DETERMINATION OF SAMPLE SIZE

7.1 STATISTICAL DESIGN - MODEL

This is a Phase I, open-label, dose-escalating trial to determine the MTD and the RP2D for BI 754091 in patients with solid tumours. In addition, the safety and PK profiles, biomarkers, and efficacy of BI 754091 will also be assessed.

7.1.1 Statistical design – Phase Ia (dose escalation)

The objective of the Phase Ia portion of the trial is to determine the MTD and the RP2D. The MTD is defined as the highest dose with less than 25% risk of the true DLT rate being above 0.33 (EWOC criterion) under the condition of at least one DLT observed in this trial. The Phase Ia dose-finding will be guided by a BLRM with overdose control (R13-4803).

The model is given as follows:

$$\text{logit}(p(d)) = \log(\alpha) + \beta * \log(d/d^*),$$

where $\text{logit}(p) = \log(p/(1-p))$.

$p(d)$ represents the probability of having a DLT in the first cycle at dose d , $d^* = 800$ mg is the reference dose, allowing for the interpretation of α as the odds of a DLT at dose d^* , and $\theta = (\log(\alpha), \log(\beta))$ with $\alpha, \beta > 0$ is the parameter vector of the model.

The estimated probability of a DLT at each dose level from the model will be summarized using the following intervals:

Under dosing: [0.00, 0.16)
Targeted toxicity: [0.16, 0.33)
Over toxicity: [0.33, 1.00]

The BLRM recommended dose for the next cohort is the level with the highest posterior probability of the DLT rate falling in the target interval [0.16, 0.33) among the doses fulfilling EWOC. Applying the EWOC criterion it should be unlikely (<25% posterior probability) that the DLT rate at that dose will exceed 0.33.

The MTD may be considered reached if one of the following criteria is fulfilled:

- At least one DLT observed in the trial, and either
- The posterior probability of the true DLT rate in the target interval [0.16 – 0.33) of the MTD is above 0.50, OR
- At least 15 patients have been treated in the trial, of which at least 6 at the MTD.

The SRC may recommend stopping the dose-finding phase after the criteria for MTD are fulfilled. If no DLTs are observed during the Phase Ia dose-escalation phase, the SRC may conclude that the MTD was not found and decide to include an additional number of patients at a dose of which the efficacy is considered sufficient as the dose recommended for further testing. This dose level may be equal or below the highest tested dose level.

Since a Bayesian approach is applied, a prior distribution $\pi(\theta)$ for the unknown parameter vector θ needs to be specified. This prior distribution will be specified as a mixture of two multivariate normal distributions, i.e.

$$\pi(\theta) = \varphi_1 \pi_1(\theta) + \varphi_2 \pi_2(\theta)$$

with

φ_i , $i = 1, 2$ the prior mixture weights ($\varphi_1 + \varphi_2 = 1$)

and

$$\pi_i(\theta) = \text{MVN}(\mu_i, \Sigma_i)$$

the multivariate normal distribution of the i -th component with mean vector μ_i and covariance matrix Σ_i , where

$$\Sigma_i = \begin{pmatrix} \sigma_{i,11}^2 & \sigma_{i,11}\sigma_{i,22}\rho_i \\ \sigma_{i,11}\sigma_{i,22}\rho_i & \sigma_{i,22}^2 \end{pmatrix}$$

Mixtures of prior distributions have the advantage of allowing for specification of different logistic dose-toxicity curves, therefore making the prior more robust.

